3.3 Inferential Analyses

Descriptive statistics will be used to summarize the safety and PK data. No formal hypothesis testing is planned. All efficacy analyses (unless otherwise specified) will be performed at a one-sided 5% level of significance.

- HBsAg decline ($\Delta \log_{10}$) from Day 1 to Week 16 of treatment (primary)
 - Hypothesis:
 - H₀₁: Adjusted Mean for experimental arm at Week xx minus Adjusted Mean for control arm at Week xx = 0, where xx = 2, 4, 6, 8, 10, 12, 14, and 16
 - H₁₁: Adjusted Mean for experimental arm at Week xx minus Adjusted Mean for control arm at Week xx = -1, where xx = 2, 4, 6, 8, 10, 12, 14, and 16.

- Time Points: Change from baseline until to Week 16 of treatment.
 - A general linear model for repeated measures will be used to assess HBsAg decline ($\Delta \log_{10}$), using the stratification factors as independent variables in the model (HBeAg pos [yes, no]). Baseline HBsAg level will be included as a covariate. The analysis will be based on a one-sided test at a 5% level of significance. Degrees of freedom calculation will be based on the Kenward-Roger method. The unstructured covariance matrix structure to model the within-patient errors will be selected initially. If the unstructured covariance structure leads to non-convergence, covariance matrix structure will be selected through the maximum likelihood method. The final model will then we rerun by using the reduced maximum likelihood method.
- The following covariates will be included for this model:
- i. Baseline HBsAg level
 - ii. HBeAg positive [yes, no]
 - iii. Treatment Group
 - iv. Study visit
 - v. Interaction between treatment group and study visit
- The least-squares mean change from baseline, along with corresponding 95% CI and SE for treatment arms and experimental arm versus control arm at the one-sided 0.05 level will be provided for Week 2, 4, 6, 8, 10, 12, 14 and 16 for the ITT population (with Multiple imputation). This will be repeated for ITT (with no imputation), mITT (with Multiple imputation), mITT (with no imputation), PP set (with Multiple imputation) and PP set (no imputation).
 - If applicable, this model will be re-analyzed with the genotype covariate as “sensitivity analysis”.
- Liver Fibrosis and inflammation change from baseline from Day 1 to Week 16 of treatment
 - Hypothesis:

H_0 : Adjusted Mean for experimental arm at Week xx minus Adjusted Mean for control arm at Week xx = 0, where xx = 4, 8, 12 and 16

H_1 : Adjusted Mean for experimental arm at Week xx minus Adjusted Mean for control arm at Week xx \neq 0, where xx = 4, 8, 12 and 16.
 - Time Points: Change from baseline until to Week 16 of treatment.
 - A general linear model for repeated measures will be used to assess Liver Fibrosis and inflammation parameters including ALT, AST, AST/ALT ratio, high sensitivity C-reactive protein, interleukin 6, tumour necrosis factor alpha, procollagen type III N terminal peptide (Pro C3), tissue inhibitor of metalloproteinases-1, using the stratification factors as independent variables in the model (HBeAg pos [yes, no]). Baseline Liver Fibrosis and inflammation parameters value will be included as a covariate. The analysis will be based on a two-sided test at a 5% level of significance. Degrees of freedom calculation will be based on the Kenward-Roger method. The unstructured covariance matrix structure will be selected initially. If the unstructured covariance structure leads to non-convergence, covariance matrix structure will be selected through the maximum likelihood method. The final model will then we rerun by using the reduced maximum likelihood method.

The following covariates will be included for this model:

 - i. Baseline liver fibrosis and inflammation parameters value
 - ii. HBeAg positive [yes, no]
 - iii. Treatment Group

- iv. Study visit
 - v. Interaction between treatment group and study visit
- The least-squares mean change from baseline, along with corresponding 95% CI and SE for treatment arms and experimental arm versus control arm at the two-sided 0.05 level will be provided for Week 4, 8, 12 and 16 for the Safety Set.
- If applicable, this model will be re-analyzed with the genotype covariate as “sensitivity analysis”.
- HBsAg responder rate (decrease from baseline ≥ 1.0 on the \log_{10} scale) at Week 16 of treatment and Weeks 40 of follow up. (secondary)
 - Hypothesis: H_0 : Treatment is not associated with endpoint
 H_A : Treatment is associated with endpoint
 - Time Points: Week 16 and Week 40.
 - The Pearson Chi-squared test will be used to compare the differences in proportions between the treatment groups at Week 16 and Week 40. At Week 16 and Week 40, this endpoint will consider multiplicity by a combination of a hierarchical fixed test procedure and a Hochberg procedure (see section 3.4 for more detail). The analysis will be based on a one-sided test at a 5% level of significance.
- HBsAg responder rate (decrease from baseline ≥ 0.5 on the \log_{10} scale) at 16 of treatment and Weeks 40 of follow up.
 - Hypothesis: H_0 : Treatment is not associated with endpoint
 H_A : Treatment is associated with endpoint
 - Time Points: Week 16 and Week40.
 - The Pearson Chi-squared test will be used to compare the differences in proportions between the treatment groups at Week 16 and Week 40. At Week 16 and Week 40, this endpoint will consider multiplicity considering multiplicity by a combination of a hierarchical fixed test procedure and a Hochberg procedure (see section 3.4 for more detail). The analysis will be based on a one-sided test at a 5% level of significance.
- HBsAg loss rate (% patients with HBsAg < Lower Limit of Quantification (LLOQ)/TND) at Week 16 of treatment and Week 40 of follow-up.
 - Hypothesis: H_0 : Treatment is not associated with endpoint
 H_A : Treatment is associated with endpoint
 - Time Points: Week 16 and Week40.
 - The Pearson Chi-squared test will be used to compare the differences in proportions between the treatment groups at Week 16, and Week 40. At Week 16 and Week 40, this endpoint will consider multiplicity by a combination of a hierarchical fixed test procedure and a Hochberg procedure (see section 3.4 for more detail). The analysis will be based on a one-sided test at a 5% level of significance.
- HBsAg loss rate (% patients with HBsAg < Lower Limit of Quantification (LLOQ)/TD) at Week 16 of treatment and Week 40 of follow-up.
 - Hypothesis: H_0 : Treatment is not associated with endpoint
 H_A : Treatment is associated with endpoint
 - Time Points: Week 16 and Week 40.

- The Pearson Chi-squared test will be used to compare the differences in proportions between the treatment groups at Week 16, and Week 40. At Week 16 and Week 40, this endpoint will consider multiplicity by a combination of a hierarchical fixed test procedure and a Hochberg procedure (see section 3.4 for more detail). The analysis will be based on a one-sided test at a 5% level of significance.

3.4 Multiple Comparisons and Multiplicity Adjustments.

For the analysis of secondary endpoints during the final analysis, multiplicity will be considered by using a combination of a hierarchical fixed test procedure and a Hochberg procedure.

Only if the primary endpoint is significant at 16 weeks, the key secondary endpoints “HBsAg loss rate (<LLOQ/TND and <LLOQ/TD)” and “HBsAg responder rates (B and A see section 3.2)” will be tested at the same one-sided α level of 0.05, using a Hochberg procedure at Week 16. This procedure goes as follows: the p-values will be ordered from small to large $p(1) \leq p(2) \leq p(3) \leq p(4)$. The largest p-value $p(4)$ will then be compared to $\alpha=0.05$. If significant, then all hypotheses will be rejected. If not, the next largest p-value $p(3)$ is compared to $\alpha/2=0.025$. If significant, then these hypotheses corresponding to $p(1)$, $p(2)$ and $p(3)$ are rejected. If not, the next largest p-value $p(2)$ is compared to $\alpha/3=0.017$. If significant, then both hypotheses corresponding to $p(1)$ and $p(2)$ are rejected. If not, the smallest p-value is compared to $\alpha/4=0.0125$. If significant, then only the hypothesis corresponding to the smallest p-value is rejected.

At 40 weeks, the key secondary endpoints HBsAg responder rates (B and A) and HBsAg loss rate will be tested a one-sided α level of 0.05, using a Hochberg procedure.

To calculate the power to detect a difference in HBsAg loss rate, we assumed a proportion of 0.5% in the placebo arm, and of 10% in the experimental arm. A trial including 49 patients results in a power of about 55% for this endpoint (using an un-pooled estimate of the variance), using a one-sided α of 0.05.

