## **11. Statistical Methods and Determination of Sample Size**

### **11.1. Statistical Analysis Plan and General Statistical Methods**

All data will be handled and processed according to the sponsor's representative (Novotech [Australia] Pty Ltd) SOPs, which are written based on the principles of GCP.

A Statistical Analysis Plan (SAP) containing the detailed planned statistical methods will be finalized prior to locking of the study database for the interim and final analysis and will form the basis for the programming of the displays and analyses of the final study data. All statistical calculations will be performed using SAS® (SAS Institute Inc., Cary, NC, USA) or similar software.

The statistical analyses will consist of both inferential and descriptive statistics. In general, the data will be presented by dose group. All collected and derived data will be included in the patient data listings.

All inferential analyses will be conducted at a one-sided 0.05 level of significance. Unless otherwise specified, all inferential testing will be one-sided in nature.

Continuous data, other than PK data, will be summarized by treatment group and time point using the number of observations, arithmetic mean, standard deviation, median, minimum and maximum. The coefficient of variance, geometric means and geometric coefficient of variance will also be presented for the concentration-related PK data. Categorical data will be summarized by the number and percentage of patients in each category. Unless specifically stated otherwise, the number of patients in the treatment group (for the specific analysis set) will be used as the denominator for all percentage calculations.

Baseline is defined as the last available non-missing value collected prior to the first administration of IP.

Change from baseline values will be calculated as the difference between the result at a specific time point, and the baseline value for the specific endpoint.

Missing, unused, or spurious data will be handling in the following manner:

- There will be no imputations or substitution made for missing safety data points.
- For the PK analyses, imputations will be made for missing data points.

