- This is carried out by using the SAS procedure PROC MI with the MCMC option, the seed number will be 20201113. The number of burn-in iterations will be 200, which is the default value. Nevertheless, if diagnosis plots show that the convergence has not yet occurred, this will be adjusted.
- Imputation will be repeated N=1000 times. The $\log_{10}(\text{HBsAg})$ will then be calculated for each of the data set.

SAS Code:

```
Proc mi data=new nimpute = 1000 out= mi_mvn seed= 20201113;
  mcmc nbiter =200 plots=trace ;
  By Treatment;
  Var Baseline log10(HBsAg);

Run;
```

- The difference in HBsAg ($\Delta \log_{10}$) from Day 1 to Week 16 between treatment and placebo will be analysed using a general linear model for repeated measures for each imputation.

SAS Code:

```
Proc mixed data= mi_mvn ;
  By _imputation_;
  Class ID TRT VISIT HBeAg;
  Model CHG = Baseline HBeAg TRT VISIT TRT*VISIT /
  SOLUTION CL;
  DDFM=KenwardRoger;
  Repeated VISIT /SUBJECT = ID TYPE = UN ;
  Lsmeans TRT*VISIT / DIFF CL;

Run;
```

- The parameter estimates obtained from the above are then combined and reported using SAS - Proc mianalyze procedure.

Conversion of categorical values

In some instances, continuous variables are expressed as a range (i.e. < 10). In such cases, values may be converted to the range boundary (upper or lower limit as applicable). As an example, a value of <10 may be converted to 10. Such substitutions will be clearly documented in the footnotes of relevant outputs.

There will be no imputations or substitution made for missing safety data points.

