SD: Standard Deviation. Percentages are calculated (the denominator used for the calculation) based on the number of participants in the ITT Set in each treatment group (N).

*For PCR-based Quantitative HCV Viral Load, percentages are based on the number of anti-HCV positive participants.

Programming note:

- Repeat for table 14.1.3.2 (mITT Set), table 14.1.3.3 (Safety Set) and table 14.1.3.4 (PP Set)

Table 14.1.4 Summary of Treatment Compliance (Safety set)

Category	Group 1 (N=xx)	etc.	Group x (N=xx)
n	xx	xx	xx
< 50% Compliance	xx (xx.x%)	xx (xx.x%)	xx (xx.x%)
>= 50% and =< 80% Compliance	xx (xx.x%)	xx (xx.x%)	xx (xx.x%)
> 80% Compliance	xx (xx.x%)	xx (xx.x%)	xx (xx.x%)

Source Listing: 16.2.5.2, 16.2.5.3

Table 14.2.1.1.x Summary of HBsAg by A Genotype (ITT Set)

Genotype: A

Visit Statistics	Group 1 (N=XXX)		etc.		Group x (N=XXX)	
	Actual Value	Change from Baseline	Actual Value	Change from Baseline	Actual Value	Change from Baseline
Baseline [1]						
N	XX	N/A	XX	N/A	XX	N/A
Mean	XX	N/A	XX	N/A	XX	N/A
SD	XX	N/A	XX	N/A	XX	N/A
Median	XX	N/A	XX	N/A	XX	N/A
Minimum	XX	N/A	XX	N/A	XX	N/A
Maximum	XX	N/A	XX	N/A	XX	N/A
Week 2						
N	XX	XX	XX	XX	XX	XX
Mean	XX	XX	XX	XX	XX	XX
SD	XX	XX	XX	XX	XX	XX
Median	XX	XX	XX	XX	XX	XX
Minimum	XX	XX	XX	XX	XX	XX
Maximum	XX	XX	XX	XX	XX	XX
Week xx						
n	XX	XX	XX	XX	XX	XX
Mean	XX	XX	XX	XX	XX	XX
SD	XX	XX	XX	XX	XX	XX
Median	XX	XX	XX	XX	XX	XX
Minimum	XX	XX	XX	XX	XX	XX
Maximum	XX	XX	XX	XX	XX	XX

Source Listing: 16.2.6.1

SD: Standard Deviation. N/A = Not Applicable.

[1] Baseline is defined as the average of screening and day 1 pre-dose.

Programming Note:

- Repeat for Genotype: Non A

- Repeat for table 14.2.1.1.2 (ITT set with no imputation), 14.2.1.2.1 (mITT with imputation), 14.2.1.2.2 (mITT with no imputation), 14.2.1.3.1 (PP set with imputation) and 14.2.1.3.2 (PP set with no imputation).

Table 14.2.2.x Analysis of HBsAg: Baseline to Week 16 (ITT Set)

	EYP001a 200 mg QD + NA daily (N=XXX)	Placebo + NA daily (N=XXX)
Week 2		
n	XX	XX
Mean change from baseline	XX	XX
LS Mean change from baseline	XX	XX
95% CI on LS mean change from baseline	XX,XX	XX,XX
SE on LS mean change from baseline	xx.xx	xx.xx
p-value	.xxx	.xxx
Difference in change from baseline at Week 10		
N	XX	
Mean	XX	
LS Mean	XX,XX	
95% on LS Mean	XX,XX	
SE on LS Mean	xx.xx	
p-value	.xxx	
<Repeat for Week 4,6,8,10,12,14,16>		

Source Listing: 16.2.6.1

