LS mean is derived from a general linear model for repeated measures. The covariates are treatment groups, visit, baseline HBsAg, A Genotype, HBeAg positive and the interaction term of treatment group*visit.

Covariance structure is XXX.

CI = Confidence Interval. SE = Standard Error.

Programming Note:

- Repeat for table 14.2.2.1.2 (ITT set with no imputation), 14.2.2.2.1 (mITT with imputation), 14.2.2.2.2 (mITT with no imputation), 14.2.2.3.1 (PP set with imputation) and 14.2.2.3.2 (PP set with no imputation) .

-The SAS code used to implement this analysis is given below:

```
PROC MIXED DATA=dataset;
  CLASS ID TRT VISIT HBeAg;
  MODEL CHG = Baseline HBeAg TRT VISIT TRT*VISIT / SOLUTION CL;
  DDFM=KenwardRoger;
  REPEATED VISIT /SUBJECT = ID TYPE = UN ;
  LSMEANS TRT*VISIT / DIFF CL;
  RUN;
```

Table 14.2.3.1 Summary and Analysis of HBsAg Loss Rate A (ITT Set)

Visit	Category	Statistics	EYP001a 200 mg QD + NA daily (N=XXX)	Placebo + NA daily (N=XXX)
Week 16		n	xx	xx
	HBsAg Loss	n (%) [1]	xx (xx.x %)	xx (xx.x %)
		p-value	0.XXX	

<Repeat for Week 40>

Source Listing: 16.2.6.1

p-value is based on the Person Chi-squared Test.

HBsAg Loss is defined as HBsAg value < LLOQ/TND.

[1] Number of subjects at each visit (Visit n) will be used as the denominator for the calculation of all percentages.

Programming Note:

- Only present Week 16 and Week 40 will consider multiplicity by a combination of a hierarchical fixed test procedure and a Hochberg procedure to adjust p-value.

Table 14.2.3.2 Summary and Analysis of HBsAg Loss Rate B (ITT Set)

Visit	Category	Statistics	EYP001a 200 mg QD + NA daily (N=XXX)	Placebo + NA daily (N=XXX)
Week 16		n	xx	xx
	HBsAg Loss	n (%) [1]	xx (xx.x %)	xx (xx.x %)
		p-value	0.XXX	

<Repeat for Week 40>

Source Listing: 16.2.6.1

p-value is based on the Person Chi-squared Test.

HBsAg Loss is defined as HBsAg value < LLOQ/TD.

[1] Number of subjects at each visit (Visit n) will be used as the denominator for the calculation of all percentages.

Programming Note:

- Only present Week 16 and Week 40 will consider multiplicity by a combination of a hierarchical fixed test procedure and a Hochberg procedure to adjust p-value.

Table 14.2.4.1 Summary and Analysis of HBsAg Responder Rate A (ITT Set)

Visit	Category	Statistics	Decrease from Baseline \geq 1.0 on the log10 Scale	
			EYP001a 200 mg QD + NA daily (N=XXX)	Placebo + NA daily (N=XXX)
Week 16	HBsAg Responder	n		
		n (%) [1]		
		p-value		
Week 40		n	xx	xx

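### SAP 3.3 sets every efficacy test at one-sided 5%, but the intervals, code, chi-square tests and table shells it specifies do not carry out or match that test

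*SAP*

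**What the plan says.** The significance level is consistent across both documents. Protocol 11.1 says "All inferential analyses will be conducted at a one-sided 0.05 level of significance", and SAP 3.3 says "All efficacy analyses (unless otherwise specified) will be performed at a one-sided 5% level of significance".

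The specified outputs are less consistent:

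- **Primary contrast.** SAP 3.3 asks for least-squares means with the "corresponding 95% CI and SE for treatment arms and experimental arm versus control arm at the one-sided 0.05 level". The imputation code in SAP 3.5 uses "Lsmeans TRT*VISIT / DIFF CL", and the programming note under mock Table 14.2.2.x uses "LSMEANS TRT*VISIT / DIFF CL". Neither sets an alpha option or derives a one-sided p-value. The shell has a row "95% CI on LS mean change from baseline" with two limits, and a p-value whose sidedness is not given.
- **Binary endpoints.** For responder rates at 1.0 and 0.5 log10, and for HBsAg loss by the TND and TD definitions, the alternative is "Treatment is associated with endpoint". For the responder rates the method reads "The Pearson Chi-squared test will be used to compare the differences in proportions between the treatment groups at Week 16 and Week 40", and the loss-rate text is parallel. Each is then called a one-sided 5% test. The shells (Tables 14.2.3.x and 14.2.4.x) print the Pearson p-value.
- **Use of the p-values.** SAP 3.4 makes primary significance the gate to the Week 16 secondary tests. It then compares the four binary p-values with 0.05, 0.025, 0.017 and 0.0125 on a one-sided alpha.

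**The concern.** A programmer who follows the code and shells as printed does not produce the test that the text specifies. By default the LSMEANS difference comes with a two-sided p-value and two-sided 95% limits, and so does the usual combination step after multiple imputation. The two-sided interval that corresponds to a one-sided 5% test is the 90% interval. A Pearson chi-square p-value carries no sign, so a placebo excess scores the same as an equal EYP001a excess.

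No passage says how a one-sided p-value is obtained, in which direction, or at which step after imputation. That leaves a choice between halving the printed value and using it as it stands. Made after unblinding, this choice could decide a borderline primary result and, through the gate, whether the Week 16 secondary endpoints are tested at all.

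**Working it through.** **Inputs.** SAP 2.4: assumed effect -0.9 (-1.0 × 0.9 for drop-out), SD 1.08 in both arms, t-test, one-sided 0.05, 80% power, N = 49, HBsAg loss 0.5% versus 10%. SAP 2.5: 37 and 12 patients. SAP 16.1: Week 12 SD 0.7 and the futility pair p = 0.603, difference 0.085.

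**1. Reproduce the sizing (one-sided).** SE = 1.08 × √(1/37 + 1/12) = 0.3588. Noncentrality = 0.9 / 0.3588 = 2.508 on 47 df. With critical value t(0.95) = 1.678, noncentral-t power is **79.6%**. At an exact 3:1 split, 49 is the smallest total that reaches 80%, so the plan's figure reproduces and is one-sided.

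**2. Same data, decision read two-sided.** With critical value t(0.975) = 2.012, power is **69.0%**. The gap is 79.6 - 69.0 = 10.6 points. About 62 to 63 patients would then be needed for 80%.

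**3. Where the test and the displayed interval part.** The one-sided test succeeds at a difference of -1.678 × 0.3588 = **-0.602** or lower. The 95% interval excludes zero only at -2.012 × 0.3588 = **-0.722** or lower. Between these values the specified test is significant while the printed interval includes zero. (SE is held at its design value.)

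**4. HBsAg loss, by the plan's unpooled approximation.** SE = √(0.005 × 0.995/12 + 0.10 × 0.90/37) = 0.0534, and 0.095 / 0.0534 = 1.780. One-sided: Φ(1.780 - 1.645) = **55.4%**, which reproduces the stated figure. Two-sided: Φ(1.780 - 1.960) = **42.9%**. The approximation is used here only to show which sidedness lies behind the stated figure; whether it describes the Pearson test well at such low counts is a separate matter.

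**5. Direction of the chi-square (illustration, not a forecast).** Suppose 0 of 37 on EYP001a and 2 of 12 on placebo. Chi-square = 49 × (0 × 10 - 37 × 2)² / (37 × 12 × 2 × 47) = 268,324 / 41,736 = 6.43, p = 0.011. That is below even 0.0125, so with the undirected p-value the null would be rejected although the excess is on placebo.

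**6. What the plan means by a p-value in the futility rule.** The split at 25 patients is not given; take 19:6 as an assumption. SE = 0.7 × √(1/19 + 1/6) = 0.328, and z = 0.085 / 0.328 = 0.259. The one-sided p is 0.602 and the two-sided p is 0.795. Only the one-sided p matches 0.603.

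**7. At about 25 patients.** SAP 15 records that enrolment was suspended after approximately 25 randomisations, with no split by arm. The method of steps 1 and 2 gives:

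| Assumed split | One-sided | Two-sided |
|---|---|---|
| 18:7 | 57% | 43% |
| 19:6 | 53% | 40% |
| 20:5 | 49% | 36% |

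**The case against.** The strongest reply is that the decision rule is not in doubt. One-sided 5% is repeated in Protocol 11.1, 11.3.3.1, 11.4 and 11.5 and in SAP 3.3, 3.4 and 16.1, and the primary alternative is directional. The futility pair works only with a one-sided p-value (step 6). The same code block is printed for the liver-fibrosis model, which is explicitly two-sided, so the code is a reused template and does not show intent. SAP 3.1 makes 95% the general display format for intervals, and no decision rests on an interval. A 2×2 chi-square has a signed root with an ordinary one-sided p-value. Comparing a two-sided p-value with 0.05 on the primary would be conservative, in a study that Protocol 5.4 calls exploratory.

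Most of this stands. A reader might infer that the plan as written loses about 11 points of power or really tests at 2.5%. The documents do not support that: the loss arises only if default output replaces the written rule. Nor is it a separate finding that test and interval would disagree in about 10.6% of trials; that is the same power difference restated.

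The reply does not close the gap, however. A template that serves both a one-sided and a two-sided analysis needs a stated step to tell them apart, and none is given. For the binary endpoints the written alternative is itself non-directional, so the one-sided label conflicts with the hypothesis as well as with default output. The signed root would resolve this, but the SAP does not mention it.

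**Conclusion.** The point holds as a mismatch between the specified test and the specified outputs, and it should be corrected before the unblinding that SAP 16.1 places after the Week 16 database lock. It does not show that the design is underpowered: under the written rule the primary has 79.6% power by the sizing test. The 69.0% (primary) and 42.9% (HBsAg loss) figures are conditional on decisions being read from two-sided output.

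The clearest defect is in the four binary endpoints, where an undirected p-value enters one-sided Hochberg thresholds and can reject for placebo. For the primary, the practical exposure is an observed difference between -0.602 and -0.722.

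All primary figures are for the sizing t-test with effect 0.9 and SD 1.08. Power for the repeated-measures model cannot be computed, because no within-patient correlation is given. Figures at about 25 patients depend on the assumed split.

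**What to change.** 1. **Primary.** In SAP 3.3 and 3.5, state that the p-value is one-sided in the direction of greater decline on EYP001a and is derived from the t statistic after the imputations are combined. Report a two-sided 90% interval, or a one-sided 95% upper bound, for the treatment difference. Set alpha in the PROC MIANALYZE step as well as in LSMEANS for the no-imputation runs; changing LSMEANS alone would leave the imputation-combined primary interval at 95%. A 95% interval may stay if labelled descriptive.
2. **Binary endpoints.** For all four, write a directional alternative (higher rate on EYP001a) and use a one-sided statistic, such as the signed root of the chi-square, for the p-values that enter Hochberg.
3. **Labels.** Mark efficacy p-values as one-sided in Tables 14.2.2.x to 14.2.4.x and in the futility rule. The Table 14.2.2.x ITT outputs are scheduled for the futility meeting, so the DSMC should not have to infer which p-value it is reading.

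The cost is a few sentences, one option in each procedure and some shell labels; no new data or patients are needed. Separately, the printed code has DDFM standing alone after the semicolon; it belongs among the MODEL options. That correction has no bearing on sidedness.

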#### *11.3.3.2. Secondary Efficacy*

HBsAg responder rate (decrease from baseline  $\geq 1.0$  on the  $\log_{10}$  scale and decrease from baseline  $\geq 0.5$  on the  $\log_{10}$  scale) and HBsAg loss rate (proportion of HBsAg < LLOQ) at Week 16 of treatment and Week 20, Week 28 and Week 40 of follow-up will be analysed as key secondary endpoints at 16 weeks, and 40 weeks. Proportion of patients of Target not detected will be analysed as exploratory endpoint. HBsAg responder rate (decrease from baseline  $\geq 0.5$  on the  $\log_{10}$  scale) will also be analysed at Week 12 of treatment. At 16 and 40 weeks, these endpoints will be analysed taking into account multiplicity by a combination of a hierarchical fixed test procedure and a Hochberg procedure (See [Section 11.4.2](#)), using a this Pearson Chi-square test. At other timepoints, analyses for these two endpoints will be descriptive.

Relapse rate HBsAg (% patients who became negative [HBsAg < LLOQ], then increased with HBsAg > LLOQ) at Week 16 of treatment period and Weeks 20, 28 and 40 during the follow-up period will be summarized by frequency counts and percentages.

Virologic failure rate (breakthrough) of HBV DNA (% patients with a confirmed quantifiable HBV DNA increase of  $\geq 1\log_{10}$  HBV DNA copies/mL above LLOQ) assessed at Weeks 16 of treatment, 20, 28 and 40 during follow up period will be summarized by frequency counts and percentages.

HBV-pgRNA decline ( $\Delta \log_{10}$ ) and HBcrAg decline ( $\Delta \log_{10}$ ) from Day 1 to Weeks 4, 8, 12 and 16 of the treatment period and Week 40 of maintenance period, HBeAg quantification for HBeAg positive patients and changes at Week 16 of treatment and Week 40 of follow-up and Fibroscan VCTE change from screening value to the Weeks 16 and 40 or ET visit will be summarized through descriptive statistics.

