2.5 Randomization

Sequential screening numbers will be assigned to patients at the time of informed consent signing. As they are enrolled into the study and after eligibility on Day -3 at the earliest and prior to dosing on Day 1 at the latest, patients will be assigned to a unique randomization number which are randomly assigned to treatment according to the specified randomization scheme.

The randomization schedule will be computer-generated before the start of the study.

An Interactive Web Response System (IWRS) will be employed to manage patient and treatment assignments.

Patients will be randomized prior to study drug (EYP001a or placebo and NA) administration on Day 1 in the ratio of approximately 3:1 (37:12) into 2 arms:

- Experimental Arm: EYP001a 200 mg QD + NA daily (37 patients)
- Control Arm: Placebo + NA daily (12 patients)

The ratio will be controlled through block randomization.

Patients will also be stratified per HBeAg status, based on medical history HBeAg value or established during screening, to obtain a balanced randomization to both study arms.

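### The HBsAg responder tests ignore the HBeAg stratum used in randomisation, which makes them conservative and costs roughly 0 to 10 points of power, depending on how prognostic HBeAg is

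*SAP*

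**What the plan says.** SAP 2.5 describes the allocation: "Patients will also be stratified per HBeAg status, based on medical history HBeAg value or established during screening". It also states that "The ratio will be controlled through block randomization", and gives the allocation as "in the ratio of approximately 3:1 (37:12) into 2 arms". Protocol 4.1 expects HBeAg-negative and HBeAg-positive patients in a 7:3 ratio.

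SAP 3.3 puts HBeAg in the repeated-measures model for the primary endpoint and in the liver fibrosis and inflammation models. For responder A (fall of at least 1.0 log10) and responder B (at least 0.5 log10), the same section says "The Pearson Chi-squared test will be used to compare the differences in proportions between the treatment groups at Week 16 and Week 40", and adds "The analysis will be based on a one-sided test at a 5% level of significance". Protocol 11.3.3.2 names the same test: "using a this Pearson Chi-square test". SAP 3.4 handles multiplicity by "using a combination of a hierarchical fixed test procedure and a Hochberg procedure", with Week 16 steps from 0.05 down to 0.0125.

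Mock tables 14.2.4.1 and 14.2.4.2 show two arms and a Pearson p-value. HBeAg subgroups are listed among the general output columns in SAP 3.7, for description only. No stratified analysis of the responder endpoints is planned, even as a sensitivity analysis.

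**The concern.** The responder endpoints are cut from the same HBsAg change that the primary model analyses with HBeAg as a covariate. The SAP gives no reason for adjusting one and not the other.

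The Pearson test estimates its variance from the overall response rate, which includes the difference between HBeAg strata. Stratified allocation has largely removed that component from the treatment comparison. If HBeAg predicts response, the estimated standard error is therefore too large, the test rejects too rarely and power is lost. With 12 planned controls, and enrolment suspended at about 25 randomisations (SAP 15), little power can be spared.

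**Working it through.** **Inputs.** From the documents: 37:12 allocation, one-sided 5%, 30% HBeAg-positive. Assumed, because the documents are silent: block size 4, responder rates, and the HBeAg odds ratio (OR, positive against negative), taken as equal in both arms.

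**The plan's own figure.** The only secondary power stated is about 55% for HBsAg loss, 0.5% against 10% (SAP 2.4). With un-pooled variance:
- SE = sqrt(0.005×0.995/12 + 0.10×0.90/37) = 0.0534
- 0.095/0.0534 = 1.780, and Φ(1.780 − 1.645) = 55.4%

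It reproduces, as an unstratified calculation. No power is stated for responders.

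**Tests compared.** Each rejects when z > 1.645.
- Pearson: z = (pA − pC) / sqrt[p(1−p)(1/nA + 1/nC)], with p the overall rate.
- CMH: z = Σ(a − nA·m/n) / sqrt[Σ nA·nC·m(n−m) / (n²(n−1))], summed over HBeAg strata, with a the active responders, m all responders and n the stratum size.

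**Size by hand, common rate 30%.** The stratum rates solve 0.7p₋ + 0.3p₊ = 0.30 at the given OR. For OR 10: 0.7×0.153 + 0.3×0.644 = 0.300. The total variance is 0.30×0.70 = 0.21, and the between-stratum part is 0.3×0.7×(p₊−p₋)² = 0.21(p₊−p₋)². The within-stratum share is therefore R = 1 − (p₊−p₋)², and approximate size is P(Z > 1.645/√R). Exact figures enumerate the binomial outcomes, averaged over stratified blocks.

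| OR | p₋, p₊ | R | Approx. size | Exact Pearson | Exact CMH |
|---|---|---|---|---|---|
| 1 | 30%, 30% | 1 | 5.0% | 4.5% | 4.4% |
| 3 | 22.8%, 46.9% | 0.942 | 4.5% | 4.0% | 4.5% |
| 5 | 19.4%, 54.7% | 0.876 | 3.9% | 3.5% | 4.6% |
| 10 | 15.3%, 64.4% | 0.759 | 3.0% | 2.6% | 4.7% |

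The exact Pearson values sit slightly below the approximation because counts are discrete (4.5% even at OR 1).

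**Power, N = 49, Pearson → CMH (%), averaged over stratified blocks.** Differences were taken before rounding.

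| Control v active | OR 1 | OR 3 | OR 5 | OR 10 |
|---|---|---|---|---|
| 5% v 30% | 61.1→61.8 (+0.7) | 61.0→64.1 (+3.0) | 61.0→66.1 (+5.1) | 61.6→71.7 (+10.1) |
| 10% v 40% | 67.6→66.9 (−0.7) | 68.2→69.7 (+1.5) | 68.2→72.2 (+4.0) | 68.8→77.1 (+8.3) |
| 20% v 50% | 61.6→60.3 (−1.4) | 61.5→62.3 (+0.7) | 61.3→65.0 (+3.7) | 62.1→69.4 (+7.2) |
| 10% v 50% | 88.1→87.2 (−1.0) | 88.6→88.8 (+0.2) | 88.8→90.3 (+1.5) | 89.6→93.0 (+3.3) |

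If HBeAg-positive patients respond less often (OR 0.2 or 0.1), the gain is 0.8 to 4.8 points. With 25 patients it is about 2 points at OR 3, 4 to 5 at OR 5 and 8 to 10 at OR 10.

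**Sensitivity to stratum balance.** At OR 10 and 5% v 30%, strata of 26+11 active and 8+4 control (negative + positive) give +14.7 points; 26+11 and 9+3 give +5.5. One control patient makes that difference.

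**The case against.** The strongest objection is that the size of the loss rests on numbers the documents do not contain. That stands. A reader who assumes stark stratum rates could infer a loss of 5 points or more whenever HBeAg matters at all. For example, 80%/30% active against 40%/5% control (HBeAg-positive/negative) gives 64.9% → 70.1% at 27+10 v 9+3. But those rates imply ORs of 9.3 and 12.7. Moving one active patient between strata (26+11 v 9+3) cuts that gain to 0.6 points. At OR 3 the average loss is only 0 to 3 points.

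A reader might also carry the argument over to HBsAg loss, which uses the same test. The figures do not support this. With no control losses, 7 of 37 active losses gives z = 1.63 and 8 of 37 gives 1.76, so at least 8 are needed when 3.7 are expected. Exact Pearson power at 0.5% v 10% is 2.6% at 37:12 with no HBeAg effect. CMH averaged over blocks reaches only about 4 to 8%. Sparse counts cause this, not the missing stratum.

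An exact conditional stratified test may look like the natural small-sample choice, but it lowers power below Pearson in most scenarios examined. In the 80%/30% v 40%/5% example it gives 54.0% against Pearson's 64.9%; for HBsAg loss it gives 0.3%.

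Three further points stand. The error is on the safe side for false positives. The protocol names the Pearson test, so the SAP does not deviate from it. All power figures are for single tests at 0.05; the effect through the whole Hochberg procedure was not computed.

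None of this supplies a reason to ignore the stratum for the responder rates.

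**Conclusion.** The point holds for responder rates A and B at Weeks 16 and 40, and is modest. If HBeAg is prognostic, the planned test is conservative and loses about 0 to 3 points of power at OR 3, 1.5 to 5 at OR 5 and 3 to 10 at OR 10. If it is not, stratifying moves power by −1.4 to +0.7 points. The trade favours stratifying.

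This rests on assumed responder rates, an OR common to both arms, the protocol's 7:3 HBeAg ratio and blocks of 4; chance balance among the controls can move any single trial well outside these averages. There is no inflation of type I error and no departure from the protocol, and no claim is made for the HBsAg loss tests.

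**What to change.** Before unblinding, which SAP 16.1 places after the Week 16 database lock:
- In SAP 3.3, replace the Pearson test for responder rates A and B with a one-sided asymptotic CMH test stratified by HBeAg, using the value on which the patient was randomised.
- Update the footnotes of tables 14.2.4.1 and 14.2.4.2.
- Record the change from Protocol 11.3.3.2 in SAP section 15.

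Do not add an exact conditional fallback, and do not extend this change to HBsAg loss on these grounds. A stratum without responders simply contributes nothing to the statistic.

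The cost is a few lines of SAP text and a small programming change. The largest power cost found at N = 49 in the block-averaged comparisons is 1.4 points, with no HBeAg effect.
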